2. INTRODUCTION

This SAP provides the detailed methodology for summary and statistical analyses of the data collected in Study C4591030. This document may modify the plans outlined in the protocol; however, any major modifications of the primary endpoint definition or its analysis will also be reflected in a protocol amendment.

2.1. Study Objectives, Endpoints, and Estimands

The estimands corresponding to each primary, secondary, and exploratory objective are described in [Table 2](#).

In the primary safety objective evaluations, missing AE start dates will be imputed according to Pfizer safety rules ([Section 5.3](#)). No other missing information (eg, missing e-diary data) will be imputed in the safety analysis.

The estimands to evaluate the immunogenicity objectives are based on the evaluable immunogenicity populations (see [Section 4](#) for definition). These estimands estimate vaccine effect in the hypothetical setting where participants follow the study schedules and protocol requirements as directed. Missing serology results will not be imputed. Immunogenicity results that are below the LLOQ, denoted as BLQ, will be set to $0.5 \times \text{LLOQ}$ in the analysis; this may be adjusted once additional data on the assay characteristics become available.

Table 2. List of Primary, Secondary, and Exploratory Objectives, Endpoints, and Estimands

Objectives	Estimands	Endpoints
Primary Safety Objective:	Primary Safety Estimands:	Primary Safety Endpoints:
To describe the safety profile of BNT162b2 when coadministered with SIV	In participants receiving 1 dose of BNT162b2 and SIV or saline and having safety follow-up after vaccination from each vaccine group, the percentage of participants reporting: 
 Local reactions within 7 days after each vaccination Systemic events within 7 days after each vaccination AEs within 1 month after each vaccination SAEs from the first vaccination up to 1 month after the last vaccination 	
 Local reactions (redness, swelling, and pain at the injection site) Systemic events (fever, fatigue/tiredness, headache, chills, vomiting, diarrhea, new or worsened muscle pain, and new or worsened joint pain) AEs SAEs
Primary BNT162b2 Immunogenicity Objective:	Primary BNT162b2 Immunogenicity Estimand:	Primary BNT162b2 Immunogenicity Endpoint:
To demonstrate that the immune responses elicited by BNT162b2 when coadministered with SIV (BNT162b2+SIV) are noninferior to those elicited by BNT162b2 when administered alone	In participants in compliance with the key protocol criteria (evaluable participants): 
 GMR of full-length S-binding IgG levels 1 month after vaccination with BNT162b2 in the coadministration group to the IgG levels 1 month after vaccination with BNT162b2 in the separate-administration group 	
 Full-length S-binding IgG levels

Table 2. List of Primary, Secondary, and Exploratory Objectives, Endpoints, and Estimands

Objectives	Estimands	Endpoints
Primary SIV Immunogenicity Objective:	Primary SIV Immunogenicity Estimand:	Primary SIV Immunogenicity Endpoints:
To demonstrate that the immune responses elicited by SIV when coadministered with BNT162b2 (BNT162b2+SIV) are noninferior to those elicited by SIV when administered alone	In evaluable participants: 
 GMR of the strain-specific HAI (or H3N2-neutralizing antibody) titers 1 month after vaccination with SIV in the coadministration group to the corresponding HAI (or H3N2-neutralizing antibody) titers in the separate-administration group 	
 Strain-specific HAI titers H3N2-neutralizing antibody titers (if H3N2-HAI titers cannot be obtained)
Secondary BNT162b2 Immunogenicity Objective:	Secondary BNT162b2 Estimands:	Secondary BNT162b2 Immunogenicity Endpoints:
To describe the immune responses elicited by BNT162b2 when coadministered with SIV or administered alone	In evaluable participants from each vaccine group: 
 GMCs/GMTs at before vaccination and 1 month after vaccination with BNT162b2 GMFR from before vaccination to 1 month after vaccination with BNT162b2 	
 Full-length S-binding IgG levels SARS-CoV-2 neutralizing titers (for a subset of approximately 200 participants)
Secondary SIV Immunogenicity Objective:	Secondary SIV Immunogenicity Estimands:	Secondary SIV Immunogenicity Endpoints:
To describe the immune responses elicited by SIV when coadministered with BNT162b2 or administered alone	In evaluable participants from each vaccine group: 
 GMTs before vaccination and 1 month after vaccination with SIV GMFR in strain-specific HAI titers from before vaccination to 1 month after vaccination with SIV 	
 Strain-specific HAI titers H3N2-neutralizing antibody titers (if H3N2-HAI titers cannot be obtained)

Table 2. List of Primary, Secondary, and Exploratory Objectives, Endpoints, and Estimands

Objectives	Estimands	Endpoints
Exploratory Immunogenicity Objective:	Exploratory Immunogenicity Estimands	Exploratory Immunogenicity Endpoints:
To further describe the immune response elicited by SIIV when coadministered with BNT162b2 or administered alone	In evaluable participants from each vaccine group: 
 The percentage of participants with strain-specific HAI titers $\geq 1:40$ 1 month after vaccination with SIIV The percentage of participants with strain-specific HAI seroconversion 1 month after vaccination with SIIV The percentage of participants with H3N2 neutralization seroprotection 1 month after vaccination with SIIV The percentages of participants with H3N2 neutralization seroconversion 1 month after vaccination with SIIV 	
 Strain-specific HAI titers H3N2-neutralizing antibody titers (if H3N2-HAI titers cannot be obtained)

2.2. Study Design

This is a Phase 3, multicenter, randomized, 2-arm parallel, observer-blind study in adults 18 through 64 years of age to assess the safety and immunogenicity of a booster dose of BNT162b2 and SIIV given together compared to the vaccines given 1 month apart. Approximately 1126 participants will be randomized at a ratio of 1:1 into the coadministration group and the separate-administration group stratified by age group (18-49 years and 50-64 years) and by history of positive SARS-CoV-2 test by NAAT or rapid antigen test prior to randomization (with and without prior history of SARS-CoV-2). Assuming a 20% nonevaluable rate, there will be approximately 900 evaluable participants. Each participant will participate in the study for approximately 2 months with 3 scheduled visits.

Local reactions (redness, swelling, and pain at the injection site) occurring at the BNT162b2 or saline injection site within 7 days and systemic events (fever, headache, fatigue/tiredness, chills, vomiting, diarrhea, new or worsening muscle pain, and new or worsening joint pain) occurring within 7 days after each vaccination (Visit 1 and Visit 2) will be prompted for and collected daily by the participant in an e-diary device or application. Use of antipyretic/pain medications will also be prompted for and collected daily in the reactogenicity e-diary for 7 days after each vaccination.

AEs and SAEs will be collected from the signing of informed consent through Visit 3 (approximately 1 month after Vaccination 2).

To assess immunogenicity, approximately 30 mL of blood will be collected from all participants at 3 study visits: at Visit 1 (prior to Vaccination 1); at Visit 2 (prior to Vaccination 2); and at Visit 3 (1 month after Visit 2).

3. ENDPOINTS AND BASELINE VARIABLES: DEFINITIONS AND CONVENTIONS

3.1. Primary Endpoints

3.1.1. Primary Safety Endpoints

The primary safety endpoints are as follows:

- Local reactions (redness, swelling, and pain at the injection site) within 7 days after each vaccination.
- Systemic events (fever, fatigue/tiredness, headache, chills, vomiting, diarrhea, new or worsened muscle pain, and new or worsened joint pain) within 7 days after each vaccination.
- AEs within 1 month after each vaccination.
- SAEs from the first vaccination up to 1 month after the last vaccination.

3.1.1.1. Local Reactions

The local reactions assessed and reported in the e-diary are redness, swelling, and pain at the injection site, within 7 days after each vaccination. This section describes derivations with details for the assessment of local reactions: presence, severity level, duration, and onset day.

Presence or Absence

For each local reaction and any local reaction on any day, [Table 3](#) defines the algorithm to derive the presence of a reaction (yes or no) during the interval within 7 days after each vaccination.

Table 3. Derived Variables for Presence of Each and Any Local Reaction Within 7 Days for Each Vaccination

Variable	Yes (1)	No (0)
Presence of each local reaction on any day	Participant reports the reaction as “yes” on any day (7 days after vaccination).	Participant reports the reaction as “no” on all 7 days (after vaccination) or as a combination of “no” and missing on all 7 days (after vaccination).
Presence of any local reaction on any day	Participant reports any local reaction as “yes” on any day (7 days after vaccination).	For all 3 local reactions, participant reports “no” on all 7 days (after vaccination) or a combination of “no” and missing on all 7 days (after vaccination).

Note: Missing e-diary data will not be imputed. Participants with no e-diary data reported will not be included in the e-diary summaries.

Severity and Maximum Severity

Redness and swelling will be measured and recorded in measuring device units (range: 1 to 21) and then categorized during analysis as absent, mild, moderate, or severe based on the grading scale in Table 4. Measuring device units can be converted to centimeters according to the following formula: 1 measuring device unit = 0.5 cm. Pain at the injection site will be assessed by the participant as mild, moderate, or severe according to the grading scale in Table 4.

Table 4. Local Reaction Grading Scale

Local Reaction	Mild (Grade 1)	Moderate (Grade 2)	Severe (Grade 3)	Potentially Life Threatening (Grade 4) ^a
Pain at the injection site	Does not interfere with activity	Interferes with activity	Prevents daily activity	Emergency room visit or hospitalization for severe pain
Redness	>2.0 cm to 5.0 cm (5 to 10 measuring device units)	>5.0 cm to 10.0 cm (11 to 20 measuring device units)	>10 cm (≥21 measuring device units)	Necrosis or exfoliative dermatitis
Swelling	>2.0 cm to 5.0 cm (5 to 10 measuring device units)	>5.0 cm to 10.0 cm (11 to 20 measuring device units)	>10 cm (≥21 measuring device units)	Necrosis

- a. Only an investigator or qualified designee is able to classify a participant’s local reaction as Grade 4, after clinical evaluation of the participant or documentation from another medically qualified source (eg, emergency room or hospital record). Grade 4 local reactions will be collected on the AE case report form and assessed by the investigator using the AE intensity grading scale.

If a Grade 3 local reaction is reported in the reactogenicity e-diary, a telephone contact should occur to ascertain further details and determine whether a site visit is clinically indicated. Only an investigator or medically qualified person is able to classify a participant's local reaction as Grade 4. If a participant experiences a confirmed Grade 4 local reaction, the investigator must immediately notify the sponsor and, if it is determined to be related to the administration of the study intervention, further vaccinations will be discontinued in that participant.

For each local reaction after each vaccination, the maximum severity grade will be derived for the e-diary collection period (within 7 days after each vaccination) as follows:

Maximum severity grade = highest grade (maximum severity) within 7 days after vaccination among the severity grades reported for that local reaction in the e-diary.

Duration (First to Last Day Reported)

The duration (days) of each local reaction will be calculated as the number of days from the start of the first reported reaction to the resolution of the last reported reaction, inclusive. Resolution is defined as the last day on which the reaction is recorded in the e-diary if the reaction lasts 7 days or less, or the day the reaction ends if it persists beyond the end of the reactogenicity e-diary period following vaccination (the latter will be collected on the CRF). If there is no known date when the reaction ended, then duration will be missing (unknown). However, if a reaction is ongoing at the time of a subsequent vaccination, the end date/day for the ongoing event would be the date/day that the next vaccination is administered, which will be used for the duration computation. Participants with no reported reaction have no duration.

Onset Day

The onset day of each local reaction will be derived. Onset day is defined as the first day of reporting the reaction with any severity after vaccination.

For the onset day of each local reaction, if participants report a change in severity of the local reaction, only the first day of reporting that specific local reaction will be counted.

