8.2.3.3. Systemic Events

During the reactogenicity e-diary reporting period, participants will be asked to assess vomiting, diarrhea, headache, fatigue/tiredness, chills, new or worsened muscle pain, and new or worsened joint pain and to record the symptoms in the reactogenicity e-diary. The symptoms will be assessed by the participant as absent, mild, moderate, or severe according to the grading scale in [Table 3](#).

If a Grade 3 systemic event is reported in the reactogenicity e-diary, a telephone contact should occur to ascertain further details and determine whether a site visit is clinically indicated. Only an investigator or medically qualified person is able to classify a participant’s systemic event as Grade 4. If a participant experiences a confirmed Grade 4 systemic event, the investigator must immediately notify the sponsor and, if it is determined to be related to the administration of the study intervention, further vaccinations will be discontinued in that participant.

Table 3. Systemic Event Grading Scale

	Mild (Grade 1)	Moderate (Grade 2)	Severe (Grade 3)	Potentially Life-Threatening (Grade 4)^a
Vomiting	1-2 times in 24 hours	>2 times in 24 hours	Requires IV hydration	Emergency room visit or hospitalization for hypotensive shock
Diarrhea	2 to 3 loose stools in 24 hours	4 to 5 loose stools in 24 hours	6 or more loose stools in 24 hours	Emergency room visit or hospitalization for severe diarrhea
Headache	Does not interfere with activity	Some interference with activity	Prevents daily routine activity	Emergency room visit or hospitalization for severe headache
Fatigue/tiredness	Does not interfere with activity	Some interference with activity	Prevents daily routine activity	Emergency room visit or hospitalization for severe fatigue
Chills	Does not interfere with activity	Some interference with activity	Prevents daily routine activity	Emergency room visit or hospitalization for severe chills
New or worsened muscle pain	Does not interfere with activity	Some interference with activity	Prevents daily routine activity	Emergency room visit or hospitalization for severe new or worsened muscle pain
New or worsened joint pain	Does not interfere with activity	Some interference with activity	Prevents daily routine activity	Emergency room visit or hospitalization for severe new or worsened joint pain

Abbreviation: IV = intravenous.

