- When an AE or SAE occurs, it is the responsibility of the investigator to review all documentation (eg, hospital progress notes, laboratory reports, and diagnostic reports) related to the event.
- The investigator will then record all relevant AE or SAE information in the CRF.
- It is **not** acceptable for the investigator to send photocopies of the participant’s medical records to Pfizer Safety in lieu of completion of the Vaccine SAE Reporting Form/AE or SAE CRF page.
- There may be instances when copies of medical records for certain cases are requested by Pfizer Safety. In this case, all participant identifiers, with the exception of the participant number, will be redacted on the copies of the medical records before submission to Pfizer Safety.
- The investigator will attempt to establish a diagnosis of the event based on signs, symptoms, and/or other clinical information. Whenever possible, the diagnosis (not the individual signs/symptoms) will be documented as the AE or SAE.

Assessment of Intensity

An event is defined as “serious” when it meets at least 1 of the predefined outcomes as described in the definition of an SAE, NOT when it is rated as severe.

GRADE	If required on the AE page of the CRF, the investigator will use the adjectives MILD, MODERATE, SEVERE, or LIFE-THREATENING to describe the maximum intensity of the AE. For purposes of consistency, these intensity grades are defined as follows:	
1	MILD	Does not interfere with participant's usual function.
2	MODERATE	Interferes to some extent with participant's usual function.
3	SEVERE	Interferes significantly with participant's usual function.
4	LIFE-THREATENING	Life-threatening consequences; urgent intervention indicated.

Assessment of Causality

- The investigator is obligated to assess the relationship between study intervention and each occurrence of each AE or SAE. The investigator will use clinical judgment to determine the relationship.
- A “reasonable possibility” of a relationship conveys that there are facts, evidence, and/or arguments to suggest a causal relationship, rather than a relationship cannot be ruled out.
- Alternative causes, such as underlying disease(s), concomitant therapy, and other risk factors, as well as the temporal relationship of the event to study intervention administration, will be considered and investigated.
- The investigator will also consult the IB and/or product information, for marketed products, in his/her assessment.

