3.1.1.2. Systemic Events (Systemic Event Symptoms and Fever)

The systemic events assessed and recorded in the e-diary are fever, fatigue/tiredness, headache, chills, vomiting, diarrhea, new or worsened muscle pain, and new or worsened joint pain within 7 days after each vaccination. The derivations for systemic events will be handled similarly to the way local reactions are handled for presence of event, severity level, duration, and onset day (see [Section 3.1.1.1](#)).

The systemic events will be assessed by the participant as mild, moderate, or severe according to the grading scale in [Table 5](#).

If a Grade 3 systemic event is reported in the reactogenicity e-diary, a telephone contact should occur to ascertain further details and determine whether a site visit is clinically indicated. Only an investigator or medically qualified person is able to classify a participant's systemic event as Grade 4. If a participant experiences a confirmed Grade 4 systemic event, the investigator must immediately notify the sponsor and, if it is determined to be related to the administration of the study intervention, further vaccinations will be discontinued in that participant.

Table 5. System Event Grading Scale

Systemic Event	Mild (Grade 1)	Moderate (Grade 2)	Severe (Grade 3)	Potentially Life Threatening (Grade 4) ^a
Vomiting	1 to 2 times in 24 hours	>2 times in 24 hours	Requires IV hydration	Emergency room visit or hospitalization for hypotensive shock
Diarrhea	2 to 3 loose stools in 24 hours	4 to 5 loose stools in 24 hours	6 or more loose stools in 24 hours	Emergency room visit or hospitalization for severe diarrhea
Headache	Does not interfere with activity	Some interference with activity	Prevents daily routine activity	Emergency room visit or hospitalization for severe headache
Fatigue/tiredness	Does not interfere with activity	Some interference with activity	Prevents daily routine activity	Emergency room visit or hospitalization for severe fatigue
Chills	Does not interfere with activity	Some interference with activity	Prevents daily routine activity	Emergency room visit or hospitalization for severe chills
New or worsened muscle pain	Does not interfere with activity	Some interference with activity	Prevents daily routine activity	Emergency room visit or hospitalization for severe new or worsened muscle pain

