6. ANALYSES AND SUMMARIES

6.1. Primary Endpoints

6.1.1. Primary Safety Endpoints

6.1.1.1. Local Reactions

6.1.1.1.1. Main Analysis

- Estimands: The percentage of participants reporting local reactions (redness, swelling, and pain at the injection site) within 7 days after each vaccination ([Section 2.1](#)).
- Analysis set: Safety population ([Section 4](#)).
- Analysis time point: Within 7 days after each vaccination.
- Analysis methodology: Descriptive statistics ([Section 5.2.1](#)).
- Intercurrent events and missing data: The participants without any e-diary data throughout the 7 days after vaccination will be excluded from the analysis at that particular vaccination; missing values will not be imputed.
- Reporting results: Descriptive statistics for each and any local reaction after each vaccination in each vaccine group will be presented by maximum severity and cumulatively across severity levels. Confirmed e-diary errors will be excluded from the analysis. Descriptive summary statistics will include counts and percentages of participants with the indicated endpoint and the associated 2-sided Clopper-Pearson 95% CIs.

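### Maximum reaction severity is taken from the e-diary alone, so an investigator-confirmed Grade 4 reaction other than fever is shown as Grade 3 or lower in the primary reactogenicity tables

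*SAP*

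**What the plan says.** Solicited local reactions and systemic events within 7 days of each vaccination are primary safety endpoints (SAP 3.1.1). They are tabulated by maximum severity and plotted with bars split by severity (SAP 6.1.1.1 and 6.1.1.2). SAP Tables 4 and 5 give a Grade 4 criterion for every solicited reaction except fever, which has its own temperature scale in Table 6.

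For each local reaction, SAP 3.1.1.1 sets the maximum grade to the "highest grade (maximum severity) within 7 days after vaccination among the severity grades reported for that local reaction in the e-diary". SAP 3.1.1.2 carries this over: "The derivations for systemic events will be handled similarly to the way local reactions are handled for presence of event, severity level, duration, and onset".

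On what the diary holds, redness and swelling are entered as 1 to 21 device units and then "categorized during analysis as absent, mild, moderate, or severe based on the grading scale in Table 4". Pain is graded by the participant as mild, moderate or severe. For systemic symptoms, Protocol 8.2.3.3 says "The symptoms will be assessed by the participant as absent, mild, moderate, or severe according to the grading scale".

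Grade 4 follows another route. Only an investigator or qualified designee may assign it, and footnote a to SAP Table 4 adds: "Grade 4 local reactions will be collected on the AE case report form and assessed by the investigator using the AE intensity grading scale". The footnote to Table 5 says the same for systemic events. On the AE scale in Protocol 10.3.3, Grade 4 means "Life-threatening consequences; urgent intervention indicated".

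On data errors, SAP 6.1.1.1.1 (local reactions) states: "Confirmed e-diary errors will be excluded from the analysis". SAP 6.1.1.2.1 (systemic events) has no such sentence.

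**The concern.** The plan defines a top severity grade, sends it to a different form under a different scale, and then derives maximum severity from the source that does not hold it. A programmer who follows the text has no instruction to bring the confirmed grade back. The reactogenicity tables and charts would then understate the severity of the worst reactions in a trial whose safety question is how two vaccines given together compare with the same vaccines given apart. Few such events are to be expected, so a single reclassified event could be all the Grade 4 information in a group.

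**Working it through.** No stated figure in the plan depends on this rule, so there is none to reproduce. The check has three parts.

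**1. Which grades can the diary yield?** One device unit is 0.5 cm. Under SAP Table 4, units 5 to 10 are Grade 1, 11 to 20 are Grade 2, and 21 or more is Grade 3. Readings of 1 to 4 units (at most 4 × 0.5 = 2.0 cm) fall below Grade 1. The highest possible reading is 21 × 0.5 = 10.5 cm, which is above 10 cm and so Grade 3.

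| Reaction | Highest diary entry | Resulting grade | What Grade 4 requires |
|---|---|---|---|
| Redness | 21 units | 3 | Necrosis or exfoliative dermatitis |
| Swelling | 21 units | 3 | Necrosis |
| Pain | Severe | 3 | Emergency room or hospital care for it |
| Vomiting | Severe | 3 | Emergency room or hospital care for hypotensive shock |
| Other systemic symptoms | Severe | 3 | Emergency room or hospital care for the symptom |
| Fever | Temperature | Top band reachable | Table 6 band above 40.0 °C |

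Fever is therefore the exception. For redness and swelling, Grade 4 is not a matter of diameter, so a confirmed case could carry a diary grade below 3. A participant with no diary data for the 7 days is left out of the table altogether (SAP 6.1.1.1.1 and 6.1.1.2.1).

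**2. Does the AE form preserve the Grade 4?** Not reliably. An emergency room visit for severe headache that is not life-threatening is Grade 4 in SAP Table 5. On the AE scale it fits Grade 3, significant interference with usual function, unless the investigator judges it life-threatening. Hypotensive shock or necrosis could be Grade 4 on both scales. The two scales agree for some events and not for others.

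**3. Does any step merge the sources?** SAP 6.1.1.1 and 6.1.1.2 contain none. By contrast, the duration rule in SAP 3.1.1.1 does draw on the CRF when a reaction outlasts the diary. The document names a CRF source where it wants one, and for severity it names none.

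**Illustration of size.** Inputs: x Grade 4 cases (assumed; the documents give no rate) and n participants in a group with diary data. The plan randomizes 563 per group; 450 is shown only as a smaller denominator. Clopper-Pearson limits, the SAP's own method, are: lower = the 2.5% quantile of Beta(x, n − x + 1), taken as 0 when x = 0; upper = the 97.5% quantile of Beta(x + 1, n − x). For x = 0 the upper limit is 1 − 0.025^(1/n), which is 1 − 0.025^(1/563) = 0.65%.

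| x | n = 563 | n = 450 |
|---|---|---|
| 0 (present rule, whatever occurs) | 0.00% (0 to 0.65) | 0.00% (0 to 0.82) |
| 1 | 0.18% (0.00 to 0.99) | 0.22% (0.01 to 1.23) |
| 2 | 0.36% (0.04 to 1.28) | 0.44% (0.05 to 1.60) |
| 3 | 0.53% (0.11 to 1.55) | 0.67% (0.14 to 1.94) |

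**The case against.** The separation of sources is deliberate and stated. AEs and SAEs are themselves primary safety endpoints, severe AEs are summarized or listed, SAEs are listed individually, an admission to hospital meets the SAE definition, and a confirmed Grade 4 reaction must be notified to the sponsor at once. All of that stands. It rules out four stronger readings that a reader might infer:

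- *The event disappears from the safety report.* It does not. What is affected is its grade in the reactogenicity display.
- *A Grade 4 row is printed that can only be zero.* The documents show no table shells. If the diary tables stop at severe, no false zero is printed, although the event is still shown at a lower grade.
- *No source ever carries the Grade 4.* Some Table 4 and 5 criteria could also be Grade 4 on the AE scale. Protocol 8.10 also provides an unscheduled-visit CRF page on which pain and systemic events are assessed against the reactogenicity grades. It speaks of a suspected Grade 4 being reported in the diary, which fits poorly with a scale ending at severe, but confirmation still takes place outside the diary. The visit can be omitted, and the SAP does not use the page.
- *Mistyped temperatures will be counted as fever above 40.0 °C.* The text does not show this. A fever that high needs confirmation by a qualified person, Protocol 8.10 includes a check for entry errors, and SAP 6.1.1.2.2 summarizes duration and onset like the local-reaction analyses, which exclude confirmed errors. The missing sentence in 6.1.1.2.1 is a small inconsistency.

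The objection does not supply a rule that returns the confirmed grade to the maximum-severity derivation.

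**Conclusion.** The point holds as a gap in the derivation. Followed literally, SAP 3.1.1.1 and 3.1.1.2 cannot yield a grade above 3 for any solicited reaction except fever, so a confirmed Grade 4 is shown as Grade 3 or lower in a primary safety table, while remaining in the AE tables at whatever intensity the AE scale gives it. The conclusion rests on the written diary options, since the diary screens are not in the documents.

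The practical size is unknown. The percentages above depend on assumed case counts and, at n = 563, on every randomized participant supplying diary data. The endpoint is descriptive: no hypothesis test, alpha level or sample size is affected. The correction is worth making because it is cheap and concerns the most severe reactions in the comparison.

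**What to change.** - In SAP 3.1.1.1 and 3.1.1.2, define maximum severity as the higher of the e-diary grade and any investigator-confirmed Table 4 or Table 5 Grade 4 with onset within 7 days of that vaccination. Name the source: the AE CRF or the existing unscheduled-visit page of Protocol 8.10. Footnote the tables to say that these events also appear in the AE tables.
- If the CRF cannot supply the Table 4 or 5 grade, footnote the reactogenicity tables and charts to say that investigator-assigned Grade 4 is excluded, and list those events by vaccine group.
- In SAP 6.1.1.2.1, repeat the exclusion of confirmed e-diary errors, to match 6.1.1.1.1.

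The cost is a few SAP sentences and minor programming to join CRF records to the diary data. The drawback is that the same event is shown in two sets of tables, which the footnote explains.
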